#### **4.3. Nonclinical Information for CTP-543**

A series of nonclinical studies were performed with CTP-543, which evaluated the *in vitro* pharmacokinetic (PK) and metabolism properties, safety pharmacology, toxicity/toxicokinetics, and genotoxicity. All safety pharmacology and toxicity studies considered necessary for human safety assessment were conducted in compliance with Good Laboratory Practice regulations.

Further details of the nonclinical studies for CTP-543 are described in the respective Investigator's Brochure.

#### **4.4. Clinical Information for CTP-543**

To-date, nine clinical studies with CTP-543 in healthy volunteers have been completed.

In patients with moderate to severe alopecia areata, seven clinical studies have been completed or are ongoing. Further information on all the completed and ongoing clinical studies, including results of completed studies, can be found in the current CTP-543 Investigator's Brochure.

**Table 4: Clinical Trials with CTP-543 in Patients with Moderate to Severe Alopecia Areata**

| Study No. and Title   | Phase | Country   | No. of Subjects  | Dosing Regimen   | Status    |
|---|-------|---|--|--|-----------|
| Study CP543.2001: A Double-Blind, Randomized, Placebo Controlled Study to Evaluate the Safety and Efficacy of CTP-543 in Adult Patients with Moderate to Severe Alopecia Areata     | 2     | United States   | 149 adult patients with moderate to severe alopecia areata
4 mg BID: 30
8 mg BID: 38
12 mg BID: 37
Placebo BID: 44 | Cohort 1: 4 mg BID CTP-543 or matching placebo for 24 weeks
Cohort 2: 8 mg BID CTP-543 or matching placebo for 24 weeks
Cohort 3: 12 mg BID CTP-543 or matching placebo for 24 weeks | Completed |
| CP543.2002: A Randomized Parallel-Group Study to Evaluate the Efficacy and Tolerability of Two Dosing Regimens of CTP-543 in Adult Patients with Moderate to Severe Alopecia Areata | 2     | United States   | 57 adult patients with moderate to severe alopecia areata
8 mg BID: 29
16 mg QD: 28                                      | CTP-543 dosed orally as tablets at doses of 8 mg BID or 16 mg QD for 24 weeks  | Completed |
| CP543.2003: A Randomized Parallel-Group Study to Evaluate the Efficacy and Tolerability of Two Dosing Regimens of CTP-543 in Adult Patients with Moderate to Severe Alopecia Areata | 2     | United States
Canada                               | 66 adult patients with moderate to severe alopecia areata
12 mg BID: 34
24 mg QD: 32                                     | CTP-543 dosed orally as tablets at doses of 12 mg BID or 24 mg QD for 24 weeks   | Completed |
| CP543.2004: A Randomized Parallel-Group Study to Evaluate the Efficacy and Tolerability of Two Dosing Regimens of CTP-543 in Adult Patients with Moderate to Severe Alopecia Areata | 2     | United States   | Approximately 317 adult patients with moderate to severe alopecia areata   | Part A, Period 1 and Part B:
8 mg BID CTP-543
12 mg BID CTP-543
Part A, Period 2:
8 mg BID CTP-543
4 mg BID CTP-543
matching placebo                                     | Ongoing   |
| CP543.3001: A Double-Blind, Randomized, Placebo-Controlled Study to Evaluate the Efficacy and Safety of CTP-543 in Adult Patients with Moderate to Severe Alopecia Areata           | 3     | United States, Canada, Europe (select EU countries)   | 706 adult patients with moderate to severe alopecia areata   | 8 mg BID CTP-543
12 mg BID CTP-543 or matching placebo  | Completed |
| CP543.3002: A Double-Blind, Randomized, Placebo-Controlled Study to Evaluate the Efficacy and Safety of CTP-543 in Adult Patients with Moderate to Severe Alopecia Areata           | 3     | United States, Canada, Europe (Poland, France, Spain, | 517 adult patients with moderate to severe alopecia areata   | 8 mg BID CTP-543
12 mg BID CTP-543 or matching placebo  | Completed |

| Study No. and Title  | Phase | Country                 | No. of Subjects         | Dosing Regimen  | Status  |
|--|-------|-------------------------|-------------------------|---|---------|
|  |       | Germany,
Hungary)    |                         |   |         |
| CP543.5001: A Multicenter,
Open-Label, Extension Study to
Assess the Long-Term Safety
and Efficacy of CTP-543 in
Adult Patients with Moderate to
Severe Alopecia Areata | 2/3   | United States
Canada | Approximately
1,100* | CTP-543 dosed orally
as tablets at doses of 8
mg BID or 12 mg
BID** for up to 276
weeks | Ongoing |

\*In addition, eligible patients from Study CP543.2004 were eligible to enroll in this study following 24 weeks of treatment.

\*\* Following implementation of urgent safety measures, only the 8 mg BID dose will be administered

## **5. ETHICS**

The procedures set out in this study protocol, pertaining to the conduct, evaluation and documentation of this study, are designed to ensure that the Sponsor and the Investigator abide by Good Clinical Practice (GCP), including but not limited to Title 21 Code of Federal Regulations (CFR) Parts 50, 56, and 312, and the Declaration of Helsinki, International Council for Harmonisation Guidelines, and local regulations governing the conduct of clinical studies.

The Investigator is responsible for protecting the rights, safety, and welfare of patients under his/her care, and for the control of the medications under investigation. All ethical, regulatory, and legal requirements must be met before the first patient is enrolled in the study.

### **5.1. Ethics Committee (EC)**

The Ethics Committee (EC) will meet all regulatory authority requirements governing ECs according to local regulations (e.g., ICH E6 CFR, Title 21, Part 56). The study protocol and any amendments, the Sponsor's approved informed consent form(s) (ICF), patient information sheets, patient recruitment materials, and other appropriate documents will be submitted to the EC for review and approval. Following review of the submitted materials a copy of the written and dated approval/favorable opinion will be forwarded to the Sponsor (or designee).

### **5.2. Written Informed Consent**

Prior to performing any study-related activities under this protocol, written informed consent with the approved ICF must be obtained from the patient.

The ICF, as specified by the clinical site's EC, must follow the Protection of Human Subjects regulations listed per local regulations. The background of the proposed study, the procedures, the benefits and risks of the study, and that study participation is voluntary must be explained to the patient. The patient must be given sufficient time to consider whether to participate in the study.

A copy of the ICF, signed and dated by the patient, must be given to the patient. Confirmation of a patient's informed consent must also be documented in the patient's source documentation prior to any testing under this protocol. The original signed consent form will be retained with the study records.

All ICFs used in this study must be approved by the appropriate EC and by the Sponsor. The ICF must not be altered without the prior agreement of the relevant EC and the Sponsor.

## 6. STUDY OBJECTIVES

The overall objectives of the study are to evaluate long-term safety of CTP-543 and to assess long-term effects of CTP-543 on treating hair loss in adult patients with moderate to severe alopecia areata.

### 6.1. Study Design and Method of Treatment Assignment

Patients with alopecia areata who previously participated in a qualifying Phase 3 clinical trial (CP543.3001 or CP543.3002) with CTP-543 and who complete a 24-week Treatment Period on Study Medication (active or placebo), have the opportunity to enroll in this open-label extension study. At the Week 52 visit, patients will be assessed for treatment success (Responders) defined as patients having an absolute SALT score of  $\leq 20$  at Week 52. These Responders will be eligible to continue in the OLE extension for up to a maximum of one additional year. Non-responders will complete the study at Week 52. Patients will provide informed consent prior to any baseline assessments being performed. Drug will be dispensed to patients following confirmation of eligibility.

Initially, patients were assigned to receive daily treatment with CTP-543 at a dose of 8 mg BID or 12 mg BID according to the following criteria:

| Previous Treatment in Qualifying Trial | Treatment Assignment in OLE |
|--|-----------------------------|
| Placebo BID                            | 8 mg BID or 12 mg BID       |
| 8 mg BID                               | 8 mg BID                    |
| 12 mg BID                              | 12 mg BID                   |

Placebo patients were randomized via the study Interactive Web Response System (IWRS) in a 1:1 ratio to 8 mg BID or 12 mg BID. The randomization schedule was generated prior to subject enrollment from studies CP543.3001 and CP543.3002.

Following reports of thrombosis with 12 mg BID after long-term administration of CTP-543 and discussions with the US Food and Drug Administration (FDA), the 12 mg BID dose was immediately discontinued and communicated under an Urgent Safety Measure. Due to implementation of this urgent safety measure, all patients previously assigned to the 12 mg BID dose will be dose reduced to the 8 mg BID dose, should they elect to continue in the trial, for the duration of the trial up to a total of 52 weeks for non-responders or a maximum of 108 weeks for responders.

At the Week 52 visit, patients will be assessed for treatment success (Responders) defined as patients having an absolute SALT score of  $\leq 20$  at Week 52. These Responders will be eligible to continue in the OLE extension for up to a maximum of additional year. Non-responders will complete the study at Week 52. Patients should be withdrawn from the trial if, in the Investigator's opinion, continued study participation is undesirable or the risk-benefit profile has become unfavorable. Additional withdrawal criteria can be found in Section 7.3.

On all Study Visit Days, every effort should be made to schedule study visits in the morning in order for patients to dose study drug in the clinic after clinical laboratory blood draws are completed.

Patient safety will be monitored throughout the trial. During the first 12 weeks of the Treatment Period, hematology, serum chemistry, and lipids will be conducted under fasted conditions every 4 weeks, followed by an assessment every 8 weeks thereafter through completion of the trial. Serum pregnancy testing will be performed at all in-clinic visits. To minimize patient burden of additional clinic visits, urine pregnancy testing will be performed by the subject at home on

Weeks 16, 24, 32, 40, 48 and 4-weeks post the final study visit. For responders, additional home pregnancy testing will be performed at Weeks 56, 64, 72, 80, 88, 96, 104, and 4-weeks post the final study visit. The test date and result will be documented in a patient diary and brought to each in-clinic study visit by the patient. SARS-CoV-2 testing will be performed at all visits. Significant cytopenias or other hematologic abnormalities will be managed by severity through dose interruption or discontinuation, and signs and symptoms of infection will be closely monitored and treated promptly (Section 8.1). Investigators should also monitor patients for possible signs, symptoms, or exposure to tuberculosis, including any travel to high-risk countries. In cases where TB infection or exposure is suspected, TB testing should be performed. Patients who experience intolerable symptoms during treatment may discontinue the study at the discretion of the Investigator. Patients may withdraw consent at any time. At each study visit, an assessment should also be undertaken for any changes in the physical exam, or symptoms such as pain, swelling or tenderness in leg(s), persistent breathing difficulties or shortness of breath, or severe headache, that are suggestive of an increased risk of thromboembolism. Patients must be withdrawn if they have a prior history of thrombotic event(s) or experience a thromboembolic event.

Assessment of treatment response with SALT for efficacy will occur every 4 weeks for the first 12 weeks, then every 8 weeks thereafter until study completion.

## 7. SELECTION AND WITHDRAWAL OF PATIENTS

Patients eligible for enrollment in the study must meet all of the following inclusion criteria and none of the exclusion criteria.

### 7.1. Patient Inclusion Criteria

1. Written informed consent, and authorization for release and use of protected health information.
2. Have completed a 24-week Treatment Period in a previous qualifying CTP-543 clinical trial.
3. Female subjects are eligible to participate if at least one of the following conditions applies:
  - a) Is a woman of childbearing potential (WOCBP) and using a medically highly effective form of birth control with a failure rate less than 1% per year from at least 4 weeks prior to Baseline until at least 30 days following last dose of study drug.  
Examples of medically highly effective birth control methods include:
    - i. Combined (estrogen and progestogen containing) hormonal contraception (oral, patch, vaginal ring)
    - ii. Progestogen-only hormonal contraception associated with inhibition of ovulation (oral, injectable, implantable)
    - iii. Intrauterine device or intrauterine hormone-releasing system
    - iv. Bilateral tubal occlusion
    - v. Vasectomized partner (partner is the sole sexual partner of the WOCBP trial participant and the vasectomized partner has received medical assessment of the surgical success)
    - vi. Sexual abstinence (reliable as refraining from heterosexual intercourse during the above-mentioned period)
  - b) Is not a WOCBP:
    - i. Premenopausal with one of the following:
      - a. Documented hysterectomy;
      - b. Documented bilateral salpingectomy;
      - c. Documented bilateral oophorectomy.
    - ii. Postmenopausal (cessation of menses for at least 12 months prior to screening)  
Postmenopausal is defined as no menses for 12 months without an alternative medical cause. In addition, a high follicle stimulating hormone (FSH) level in the postmenopausal range may be used to confirm postmenopausal in women under 60 years old and not using hormonal contraception or hormone replacement therapy (HRT). However, in the absence of 12 months of amenorrhea, a single FSH measurement is insufficient. Females on HRT and whose menopausal status is in doubt will be required to use one of the nonestrogen hormonal highly effective contraception methods if they wish to continue their HRT during the study. Otherwise, they must discontinue HRT to allow confirmation of postmenopausal status before study enrollment
4. Male participants must:

- a. Agree to use, with their partners, male contraception (condom) and one of the highly effective contraceptive methods listed in Inclusion Criterion 5, from Baseline until at least 90 days following last dose of study drug.
- b. Refrain from donating sperm during the study and for at least 90 days after the end of the study.

5. Willing to comply with the study visits and requirements of the study protocol.

## 7.2. Patient Exclusion Criteria

1. Active scalp inflammation, psoriasis, or seborrheic dermatitis requiring topical treatment to the scalp, significant trauma to the scalp, or other scalp condition that may interfere with the SALT assessment, or untreated actinic keratosis anywhere on the body.
2. Females who are nursing, pregnant, or planning to become pregnant while in the study, and for 30 days after last dose of study medication.
3. Donation of blood at any point throughout the study and for 30 days after last dose of study medication.
4. Most recent hematologic parameters do not permit continued dosing; i.e., criteria for withholding IP have been met and have not recovered to values required to resume dosing.
5. Any medical (e.g. any prior history of thromboembolism), psychiatric, or social condition that is likely to unfavorably affect the risk-benefit of continued study participation, interfere with study compliance, or confound safety or efficacy assessments.

## 7.3. Patient Withdrawal Criteria

All patients are free to withdraw from participation in the study at any time, for any reason, and without prejudice. The Investigator must withdraw any patient from the study if the patient requests to stop participating in the study. The Investigator, Sponsor, or its designee may remove a patient from the study at any time and for any reason. In addition, patients must be withdrawn if they:

- Have a prior history of thrombotic event(s);
- Experience a thromboembolic event;
- Experience an intolerable adverse event, including but not limited to bone marrow related events characterized by protocol specified hematologic abnormalities, or a  $\geq$  Grade 3 cardiac event, or a  $\geq$  Grade 4 (other) adverse event (CTCAE v5.0 criteria) considered possibly related to study drug. Because laboratory abnormalities can occasionally occur that do not in themselves pose an unacceptable risk to subject safety (e.g., CK elevations with exercise, laboratory errors or artifacts), the occurrence of a  $\geq$  Grade 4 laboratory abnormality, or any laboratory abnormality of concern to the Investigator, will be discussed with the Medical Monitor and a determination will be made, based on a reassessment of risk-benefit for the subject, whether the subject should discontinue randomized treatment. Documentation on the determination will be maintained in the study files;
- Require a medication that is prohibited by the protocol. However, under certain circumstances, and in consultation with the Medical Monitor, short-term use of a

prohibited medication may not necessitate withdrawal when its use is unlikely to unfavorably alter the risk-benefit of subject participation or confound the study endpoints;

- Experience an adverse event of progressive multifocal leukoencephalopathy (PML) or skin cancer which are rare but potential risks of the drug;
- Do not follow guidelines specified in the protocol (i.e., is noncompliant with protocol procedures or study treatment administration);
- In the opinion of the Investigator, have any medically appropriate reason or significant protocol violation;
- Become pregnant;
- Have a serious adverse event associated with a SARS-CoV-2 infection;
- Are lost to follow up;
- Are, in the judgement of the Investigator, not exhibiting clear benefit following one full year of active treatment with CTP-543;
- In the opinion of the Investigator, feel that continued study participation is undesirable or the risk-benefit profile has become unfavorable.

Patients who withdraw or are withdrawn from the study will not be replaced.

### **7.3.1. Patient Withdrawal Procedures**

A patient who prematurely discontinues study treatment/study participation should have all Early Termination Visit assessments performed (See [Table 1](#) and [Table 2](#)).

If a patient terminates early from the study, the Investigator will record the reason(s) for early termination on the relevant electronic case report form (eCRF). The specific reason for the withdrawal should be carefully documented on the eCRF.

Adverse events resulting in patient early termination will be followed to the satisfactory resolution and determination of outcome, as ascertained by the Investigator (and/or Sponsor, or its designee); See [Section 10 Adverse Events](#). The data will be recorded on the appropriate eCRF.

## **7.4. Criteria for Study Termination**

### **7.4.1. End of Trial**

The end of the trial is defined as the date of the last visit of the last subject undergoing this trial. Within 90 days after the end of the clinical trial, the regular termination of the trial will be reported to the responsible ethics committee and competent authority according to national laws and regulations. If the trial has to be terminated early, this period shall be reduced to 15 days and the reasons clearly explained.

There are no prospective stopping criteria for this study. The Sponsor reserves the right to discontinue the study at any time for clinical or administrative reasons.

In the case of a negative change in the risk-benefit ratio, the study will not be continued even if adaptations to the maximum insured amount are requested.

Any termination required by the Sponsor must be implemented by the Investigator, if instructed to do so, in a time frame that is compatible with the patient's well-being.

## 8. DESCRIPTION OF STUDY TREATMENTS

### 8.1. Safety Criteria and Management for Stopping Doses

Patients who experience significant changes in their hematology laboratory values as described in [Table 5](#) should have their dose interrupted; or be discontinued from the study based on the medical judgement of the Investigator. The Medical Monitor should be consulted whenever possible prior to decisions for dose interruption or patient discontinuation from the study.

Dose interruption requirements for hematologic abnormalities are provided below.

**Table 5: Selected Hematologic Thresholds for Dose Interruption**

| Neutrophil Count                    |     |
|-------------------------------------|-----|
| Less than $0.5 \times 10^9/L$       |     |
| Between $0.5$ and $1 \times 10^9/L$ |     |
| Female Hemoglobin Level             |     |
| Less than 10 g/dL                   |     |
| Male Hemoglobin Level               |     |
| Less than 11.5 g/dL                 |     |
| Platelet Count                      |     |
| Less than $75 \times 10^9/L$        |     |
| Greater than $750 \times 10^9/L$    | 600 |

Upon dose interruption, the parameters that triggered the interruption should be monitored at least weekly until recovery above the threshold for dosing resumption is achieved.

Any dose interruptions for a patient should be discussed with the Medical Monitor.

Patients who are discontinued from the study should undergo an Early Termination Visit per [Section 7.3.1, Patient Withdrawal Procedures](#), and associated adverse events should follow the procedures described in [Section 10, Adverse Events](#).

Hematology, serum chemistry, and lipid parameters will be assessed under fasted conditions every 4 weeks for the first 12 weeks of the Treatment, and every 8 weeks thereafter for the remainder of the study. Serum pregnancy testing will be performed at all in-clinic visits. To minimize patient burden of additional clinic visits, urine pregnancy testing will be performed by the subject at home on Weeks 16, 24, 32, 40, 48 and 4-weeks post the final study visit. For

responders, additional home pregnancy testing will be performed at Weeks 56, 64, 72, 80, 88, 96, 104, and 4-weeks post the final study visit. The test date and result will be documented in a patient diary and brought to each in-clinic study visit by the patient. Less significant changes in laboratory values may warrant clinical intervention and the Investigator should use his/her best clinical judgement when considering a dose interruption, whether for singular or aggregate laboratory results outside of the normal range, or for other clinical signs, symptoms, or considerations that suggest dose interruption is in the best interest of the patient. Prior to a dose interruption, the laboratory values of interest should be confirmed with repeat testing at an interval deemed appropriate by the Investigator (e.g., at the next protocol-defined visit or an Unscheduled Visit). Again, the Medical Monitor should be notified whenever possible prior to decisions for dose interruption.

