**Statistical methods:**

All statistical methods are descriptive. No formal hypothesis will be tested. All confidence intervals, p-values, or any other inferential statistics provided will be exploratory in nature

*Safety Analyses:*

Safety analyses will include all patients who receive study drug. Adverse events will be coded by system organ class and preferred term with the Medical Dictionary for Regulatory Activities. Concomitant medications will be summarized by World Health Organization Drug Dictionary Anatomical-Therapeutic-Chemical classification and preferred term. Adverse events, physical examination findings, electrocardiogram, clinical laboratory information, and concomitant medications will be tabulated and summarized by treatment and dose level. By-patient listings will be provided for any deaths, serious adverse events, and adverse events leading to discontinuation of treatment.

*Efficacy Analyses:*

Efficacy analyses will include all patients who receive study drug and have at least 1 post-baseline SALT assessment in this study. Relative change in SALT score overtime will be summarized descriptively by visit, as appropriate. Additional details for statistical methods will be provided in the Statistical Analysis Plan.

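### Protocol 8.1 ends weekly monitoring on recovery above a threshold, which is the wrong direction for the one Table 5 trigger that is a high value (platelets greater than 750)

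*Protocol*

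**What the plan says.** Protocol Section 8.1 sends hematologic abnormalities to Table 5. Patients who meet a row of it "should have their dose interrupted; or be discontinued from the study based on the medical judgement of the Investigator". The table has six triggers:

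- neutrophils below 0.5 x 10^9/L
- neutrophils between 0.5 and 1 x 10^9/L
- female hemoglobin below 10 g/dL
- male hemoglobin below 11.5 g/dL
- platelets below 75 x 10^9/L
- platelets above 750 x 10^9/L, printed as "Greater than $750 \times 10^9/L"

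SAP Table 3 (Section 9.5) repeats all six, so the high-platelet trigger is intended and is not a misprint.

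Directly below Table 5 one sentence sets how long the extra monitoring lasts, with no distinction between rows: the triggering parameters "should be monitored at least weekly until recovery above the threshold for dosing resumption is achieved". The next sentence asks that any interruption be discussed with the Medical Monitor. Outside an interruption, Sections 8.1 and 9.2 schedule hematology every 4 weeks for the first 12 weeks and every 8 weeks after that.

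Most of the second column of Table 5 is not readable in the copy used here. A bare 600 stands on the high-platelet row. It is taken below as that row's resumption value, which is an assumption.

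**The concern.** The sentence is an operative safety instruction: it tells a site when it may stop weekly blood counts in a patient whose drug has been interrupted. It gives one direction, upward, for all triggers. A patient interrupted for a high platelet count recovers downward. For that patient the stated test does not separate a count that has come down from one that has not; it gives the opposite answer in each case.

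What is at stake is the frequency of monitoring. A site that applies the words as printed could stop weekly counts while platelets are still high and fall back on the routine visit schedule. The SAP mentions approximately 50 sites (Section 8.1.1), so the rule has to be read the same way by many people without inference.

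**Working it through.** No sample-size or error-rate calculation applies, and the plan states no figure to reproduce. The check is to apply the printed test to each row.

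**Inputs.** The six triggers and the monitoring sentence come from Protocol 8.1, Table 5 and the text below it. The routine hematology intervals of 4 and 8 weeks come from Protocol 8.1 and 9.2. The value 600 is the entry on the high-platelet row, assumed to be the resumption value. The counts 760 and 400 are illustrations.

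**Notation.** Let x be the current value, T the trigger and R the resumption value. The direction in the sentence is: weekly monitoring ends when x > R.

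**Low-value triggers (five rows).** Dosing is interrupted at a value below T (for the middle neutrophil row, below its upper end of 1). If R is at or above T, then at interruption x < T ≤ R, so x > R is false. It becomes true only after the value has risen past R. The test works as intended.

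**High-value trigger (one row).** Dosing is interrupted when x > 750. If R ≤ 750, then at interruption x > 750 ≥ R, so x > R is already true. It becomes false only once x falls to R or lower.

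| State of a patient interrupted for high platelets | x | Is x > R, with R = 600? |
|---|---|---|
| Day of interruption | 760 | 760 > 600: yes |
| After the count has come down | 400 | 400 > 600: no |

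With R = 600, any triggering count exceeds R by more than 750 − 600 = 150 x 10^9/L. The conclusion does not rest on 600: it holds for every R up to and including 750. A value of R above 750 would allow dosing to resume while the trigger was still met, so it is not considered.

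**Count of rows.** The direction fits 5 of 6 triggers and is reversed for 1 of 6.

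**What the literal reading would cost in monitoring.** Between two routine visits 8 weeks apart, a weekly rule adds at least 8 − 1 = 7 counts. Between two visits 4 weeks apart it adds at least 4 − 1 = 3. Those are the counts that could be lost if weekly monitoring ended on the day of interruption.

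**The case against.** The strongest reply is that the sentence requires recovery, and a count of 760 on the day dosing stops for a high count is not a recovery from anything. A sensible investigator would see the intent. Section 8.1 also asks for discussion with the Medical Monitor, and Section 9.5 provides unscheduled visits for hematology before and after an interruption. This stands as a reason to expect few literal misapplications. It does not change the fact that the sentence names a direction and that the direction is wrong for one row. The discussion in Section 8.1 concerns the interruption; no passage expressly requires agreement before weekly counts stop.

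Four stronger readings are tempting, and the documents do not support them.

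- *That dosing may resume at an unresolved high count, or may never resume after recovery.* The sentence governs the length of weekly monitoring. The resumption condition itself is apparently in the second column of Table 5, which may carry its own direction. If it shows a *less than* sign beside 600, the resumption rule is sound and only the monitoring sentence conflicts with it.
- *That resumption values are missing.* An unreadable column is not an omission from the plan.
- *That exclusion criterion 4 is also faulty.* It excludes patients for whom "criteria for withholding IP have been met and have not recovered to values required to resume dosing". That wording is neutral on direction and works for high platelets as it stands.
- *That the defect bears on the thrombosis signal.* The 12 mg dose was stopped "Following reports of thrombosis with 12 mg BID after long-term administration of CTP-543", but neither document links those events to platelet counts above 750 or to the monitoring rule.

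**Conclusion.** The point holds as a wording error in a safety-monitoring rule, confined to the high-platelet row. The conclusion needs only that the resumption value for that row is not above 750; the 600 on the row agrees with this. Read literally, the end of weekly monitoring is satisfied at interruption and ceases to be satisfied once the count has fallen.

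Its size is one trigger of six. The documents do not say how many patients reach it, and a given patient is affected only if a site follows the printed direction over the evident intent. No statistical result depends on it: the Protocol says "No formal hypothesis will be tested", and SAP Section 9.5 uses the same triggers only to select patients for a listing. It is worth correcting because the rule is operative and the correction is almost free.

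**What to change.** Reconcile the monitoring sentence in Protocol 8.1 with the high-platelet row of Table 5, so that the direction of recovery matches the direction of the trigger. One way is to drop the single direction and refer to recovery to the resumption value that Table 5 shows for the row concerned. When doing so, the sponsor should check that any direction printed in the table's second column agrees with the revised sentence. Exclusion criterion 4 and the SAP need no change. The thresholds and resumption values themselves are for the sponsor's medical team, and none is proposed here.

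The cost is one sentence and a clarification letter to sites. Protocol 12.4 treats any permanent change as an amendment, so the text change can go into the next one; the sponsor would decide whether it counts as administrative.
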